### 8.2. Enrollment Visit (Day 1)

The purpose of the Enrollment Visit is to obtain written informed consent and/or assent (if applicable), if not previously obtained remotely and/or during a separate clinic visit (prior to performing any other study procedures), confirm there are no changes in the participant's eligibility since pre-screening, and initiate vaccination or placebo administration.

The following procedures and assessments will be conducted during this visit:

#### Pre-Vaccination

- Obtain written informed consent and/or assent, if not obtained prior to visit
- Collect demographics
- Medical History and Physical Exam by a study physician or other qualified medical professional
- Urine pregnancy test for female participants of child-bearing potential who do not self-report as pregnant
- Assessment of concomitant medications
- Vital signs (temperature, pulse rate, respiratory rate, O2 saturation, blood pressure), plus growth parameters (height and weight)
- Randomization
- Assessment of HA/MCD participant access to an epinephrine auto injector; distribution of epinephrine auto-injectors (2 pack) for participants in the HA/MCD group who did not bring auto-injectors with them or bring expired auto-injectors
- Blood, nasal swab, and urine sample collections for assessments defined in [Appendix 3: Schedule of Events](#)
- Assessment of AEs

- **Diary Overview, Training, & Distribution:** Participants will be provided access to an electronic 7-day diary to aid in recording solicited local and systemic reactions to the vaccine, as well as symptoms of a potential allergic reaction, unsolicited AEs, and concomitant medications, including start and stop dates. The diary will include instructions for participants on how to take an oral temperature and how to measure injection site reactions. A paper copy of the diary may be provided for participants who do not have a device to access the electronic diary or as a backup collection tool. A member of the study team will review the information in the diary with the participant, including how to use and access the electronic diary.

Following sample collection, participants will be randomized and will receive their initial vaccination or placebo dose. Following vaccination or placebo administration (as assigned), the study participant will be observed for 90 minutes for AEs, including examination of the injection site, and have vital sign measurements and additional urine and blood samples collected 1-hour post-vaccination and/or 30-60 minutes after the onset of an allergic reaction.

During the 90-minute observation period, all AEs will be recorded, and AEs judged by an investigator to constitute an allergic reaction, even if not severe, will be documented on the appropriate eCRFs. In the event of an allergic reaction occurring more than 1 hour post vaccination, urine and blood samples will be collected, per [Appendix 3: Schedule of Events.](#)

In the event of a systemic allergic reaction, participants will be treated with rescue medications ([Section 7.4 Rescue Medications](#)) and observed for a minimum of 2 hours after their symptoms resolve. Vital signs will be monitored during a systemic allergic reaction. Additional urine and blood samples will be obtained prior to discharge.

To assist study participants and/or their parents/legal guardians in the identification of and steps to take in the event of an allergic reaction after they leave the study site, each participant will be provided with an Anaphylaxis Emergency Care Plan. The PI or designee shall review the symptoms and steps to take in the event of an allergic reaction, including training on how to use the epinephrine auto-injector, with the participant and/or parents/legal guardians prior to discharge.

### **8.3. Follow-Up Call (Day 4 ± 1 Day)**

Approximately 3 days following the participant's Enrollment Visit, the study team will call the participant to assess for AEs and review the participant diary. Any reported AEs and changes in concomitant medications will be recorded on the appropriate eCRF. Study staff will schedule the participant's next vaccination visit during the call.

### **8.4. Participants Randomized to Vaccine and No Placebo**

#### **8.4.1. Second Vaccination Visit (Day 22 or 29; -4 to +14 Days)**

Participants randomized to vaccine (no placebo) will be asked to return to clinic for the second vaccination 21 days (Day 22) or 28 days (Day 29) after their first vaccination, based on their assignment to receive the Pfizer-BioNTech COVID-19 Vaccine or Moderna COVID-19 Vaccine.

The following procedures and assessments will be conducted during this visit:

##### **Pre-Vaccination**

- Abbreviated Medical History and Targeted Physical Exam by a study physician or other qualified medical professional
- Urine pregnancy test for female participants of child-bearing potential who do not self-report as pregnant

- Assessment of concomitant medications
- Vital signs
- Blood, nasal swab, and urine sample collections for assessments defined in [Appendix 3: Schedule of Events](#)
- Assessment of AEs
- Diary Review (Dose 1) and Distribution (Dose 2)
- Distribution of epinephrine auto-injectors (2 pack) for participants in the HA/MCD group who did not bring with them or bring expired auto-injectors

Following sample collections, participants will receive their second vaccination. Following vaccination, the study participant will be observed for AEs, including examination of the vaccination site, and have vital sign measurements and additional urine and blood samples collected 1-hour post-vaccination and/or 30-60 minutes after the onset of an allergic reaction.

During the 90-minute observation period, all AEs will be recorded, and AEs judged by an investigator to constitute an allergic reaction, even if not severe, will be documented on the appropriate eCRFs. In the event of an allergic reaction, occurring more than 1 hour post vaccination, urine and blood samples will be collected, per [Appendix 3: Schedule of Events](#).

In the event of a systemic allergic reaction, participants will be treated with rescue medications ([Section 7.4: Rescue Medications](#)) and observed for a minimum of 2 hours after their symptoms resolve. Vital signs will be monitored during a systemic allergic reaction. Additional urine and blood samples will be obtained prior to discharge.

To assist study participants and/or their parents/legal guardians in the identification of and steps to take in the event of an allergic reaction after they leave the study site, each participant will be provided with an Anaphylaxis Emergency Care Plan. The PI or designee shall review the symptoms and steps to take in the event of an allergic reaction, including training on how to use the epinephrine auto-injector, with the participant and/or parents/legal guardians prior to discharge.

#### **8.4.2. Follow-Up Call (Day 25 or 32 ± 1 Day)**

Approximately 3 days following the participant's second vaccination visit, the study team will call the participant to assess for AEs and review the participant diary. Any reported AEs and changes in concomitant medications will be recorded on the appropriate eCRF. Participants will be told whether they were part of the group who received a placebo dose.

### **8.5. Participants Randomized to Receive Placebo**

#### **8.5.1. First Vaccination Visit (Day 22 or 29; -4 to + 14 Days)**

Participants randomized to placebo will be asked to return to clinic to receive their first vaccine injection, approximately 21 or 28 days, per vaccine assignment, after they received the placebo. In addition to receiving the Pfizer-BioNTech COVID-19 Vaccine or Moderna COVID-19 Vaccine, the participant will complete the same study procedures as those conducted during the Enrollment Visit, with the exception of growth parameters (Section 8.2 Enrollment Visit [Day 1]).

### **8.5.2. Follow-Up Call (Day 25 or 32 ± 1 Day)**

Following their First Vaccination Visit, participants randomized to placebo, will have a follow-up call, approximately 3 days later. The study team will call the participant to assess for AEs and review the participant diary. Any reported AEs and changes in concomitant medications will be recorded on the appropriate eCRF. Participants will be told whether they were part of the group who received a placebo dose.

### **8.5.3. Second Vaccination Visit (Day 43 or 57; -4 to +14 Days)**

Participants randomized to receive placebo during their Enrollment Visit, will complete a third clinic visit, during which they will receive their second injection of the Pfizer-BioNTech COVID-19 Vaccine or Moderna COVID-19 Vaccine, as assigned. The procedures and assessments conducted during this visit will be the same as those conducted during the Second Vaccination Visit for participants not randomized to placebo. ([Section 8.4.1 Second Vaccination Visit](#)).

### **8.5.4. Follow-Up Call (Day 46 or Day 60 ± 1 Day)**

Following their Second Vaccination Visit, participants randomized to placebo, will have a follow-up call, approximately 3 days later. The study team will call the participant to assess for AEs and review the participant diary. Any reported AEs and changes in concomitant medications will be recorded on the appropriate eCRF.

## **8.6. End of Study Call (Day 29 or 36 ± 1 Day [No Placebo] / Day 50 or 64 ± 1 Day [Placebo])**

All participants who complete their assigned vaccination regimen will complete an End of Study Visit approximately 7 days after their last vaccination. This visit will be conducted over the phone, and participants will be asked to report any new AEs and review their final participant diary.

## **8.7. Unscheduled Visits**

If a participant develops symptoms of a reaction post-visit or other concerns arise between regularly scheduled visits, participants will be instructed to contact study personnel and may be asked to return to the study site for an “unscheduled” visit. If the participant presents with symptoms for a suspected allergic reaction, the investigator—at his/her discretion, may elect to collect blood samples for the assessment of serum biomarkers and/or complement activation. Additional procedures, including the collection of samples for local labs, will follow the investigator’s elected standard of care.

## **8.8. Visit Windows**

Study visits should take place within the time limits specified above: the designated visit windows (*i.e.*  $+/- n$  days) for each scheduled visit are also indicated in [Appendix 3: Schedule of Events](#). If study visits are not conducted within the visit windows, a protocol deviation will be recorded. In the rare event a vaccination window cannot be met, vaccination may be scheduled beyond the +14-day window. If a participant becomes infected with SARS-CoV-2 or another acute illness following his/her first dose of vaccine, the second vaccination will be delivered, with allowance for a delay up to 90 days following the first dose.

## **9. Study Procedures (Protocol versions 5.0 – 8.0)**

A summary of complete study procedures is included in Tables C and D in [Appendix 3: Schedule of Events](#).

### **9.1. Recruitment & Pre-Screening (Day -14 to Day 0)**

Potential study participants may be identified by medical chart review or from a response to a study advertisement, and initially contacted by a member of the study team in person or over the phone. During this initial contact, the potential

participant's parent/legal guardian will be provided information on the study and asked to provide verbal permission for pre-screening. If a participant's parent/legal guardian provides verbal permission for pre-screening, they may be pre-screened over the phone using a standardized form to confirm eligibility. Eligible pre-screened individuals interested in participating in the study will be consented either remotely or during a clinic visit.

If it is possible to provide a physical copy of the consent and/or assent (if applicable) and verify who is consenting/assenting, remote consenting may be conducted. In the event of a remote consent, the participant's parent/legal guardian will need to return the signed consent and/or assent (if applicable) to the clinic, prior to the conduct of any study procedures. The signed consent and/or assent may be returned via an approved electronic platform, in person, and/or by mail. The process for remote consenting will be further defined in the MOP.

In the event a site does not have the ability to conduct a remote consent and/or the participant or parent/legal guardian does not have access to the methods required for remote consent, an in-person clinic visit may be scheduled to complete the consenting process. Based upon the site's policies and vaccination schedules, this may be a separate clinic visit and/or combined with the Enrollment Visit.

## 9.2. Enrollment Visit (Day 1)

The purpose of the Enrollment Visit is to obtain written informed consent and assent (if applicable), if not previously obtained remotely and/or during a separate clinic visit (prior to performing any other study procedures), confirm there are no changes in the participant's eligibility since pre-screening, and initiate vaccination or placebo administration.

The following procedures and assessments will be conducted during this visit:

### Pre-Vaccination

- Obtain written parent/legal guardian consent and participant assent (if applicable), if not obtained prior to visit
- Collect demographics
- Medical History and Physical Exam by a study physician or other qualified medical professional
- Urine pregnancy test for female participants of child-bearing potential who do not self-report as pregnant
- Assessment of concomitant medications
- Vital signs (temperature, pulse rate, respiratory rate, O2 saturation, blood pressure), plus growth parameters (height and weight)
- Randomization
- Assessment of HA/MCD participant access to an epinephrine auto injector; distribution of epinephrine auto-injectors (2 pack) for participants in the HA/MCD group who did not bring auto-injectors with them or bring expired auto-injectors
- Blood, nasal swab (participants enrolled under protocol version 8.0 will not be required to provide a nasal swab), and urine sample collections for assessments defined in [Appendix 3: Schedule of Events](#)
- Assessment of AEs
- Diary Overview, Training, & Distribution: Participants will be provided access to an electronic 7-day diary to aid in recording solicited local and systemic reactions to the vaccine, as well as symptoms of a potential allergic reaction, unsolicited AEs, and concomitant medications, including start and stop dates. The diary will include instructions for participants and/or parent/legal guardian on how to take an oral temperature and how to measure injection site reactions. A paper copy of the diary may be provided for participants who do not have a device to access the electronic diary or as a backup collection tool. A member of the study team will review the

information in the diary with the participant and/or parent/legal guardian, including how to use and access the electronic diary. The parent and or legal guardian may need to assist their child or answer for their child.

Following sample collection, participants will be randomized and will receive their initial vaccination or placebo dose. Following vaccination or placebo administration (as assigned), the study participant will be observed for 90 minutes for AEs, including examination of the injection site, and have vital sign measurements. Participants will have blood collected 30-60 minutes after the onset of an allergic reaction. Samples will not be collected 1 hour post vaccination under protocol versions 5.0 – 8.0. Sample collections post vaccination will be based on participant weight, detailed further in the MOP.

During the 90-minute observation period, all AEs will be recorded, and AEs judged by an investigator to constitute an allergic reaction, even if not severe, will be documented on the appropriate eCRFs.

In the event of a systemic allergic reaction, participants will be treated with rescue medications ([Section 7.4 Rescue Medications](#)) and observed for a minimum of 2 hours after their symptoms resolve. Vital signs will be monitored during a systemic allergic reaction.

To assist study participants and/or their parents/legal guardians in the identification of and steps to take in the event of an allergic reaction after they leave the study site, each participant will be provided with an Anaphylaxis Emergency Care Plan. The PI or designee shall review the symptoms and steps to take in the event of an allergic reaction, including training on how to use the epinephrine auto-injector, with the participant and/or parents/legal guardians prior to discharge.

### **9.3. Follow-Up Call (Day 4 ± 1 Day)**

Approximately 3 days following the participant's Enrollment Visit, the study team will call the participant to assess for AEs and review the participant diary. Any reported AEs and changes in concomitant medications will be recorded on the appropriate eCRF. Study staff will schedule the participant's next vaccination visit during the call.

During this call, the participant will be informed if they received placebo at their first injection visit (Day 1). If so, their next vaccination visit will occur within 7 days of Day 1. For participants who received vaccine on Day 1, the next vaccination visit will be scheduled to occur on Day 22 (for Pfizer) or 29 (for Moderna).

### **9.4. Participants Randomized to Receive Vaccine and No Placebo Under Protocol Versions 5.0 – 8.0**

#### **9.4.1. Second Vaccination Visit (Day 22 or 29; -4 to +14 Days)**

Participants randomized to vaccine (no placebo) will be asked to return to clinic for the second vaccination 21 days (Day 22) or 28 days (Day 29) after their first vaccination, based on their assignment to receive the Pfizer-BioNTech COVID-19 Vaccine or Moderna COVID-19 Vaccine.

The following procedures and assessments will be conducted during this visit:

##### **Pre-Vaccination**

- Abbreviated Medical History and Targeted Physical Exam by a study physician or other qualified medical professional
- Urine pregnancy test for female participants of child-bearing potential who do not self-report as pregnant
- Assessment of concomitant medications

- Vital signs
- Nasal swab (participants enrolled under protocol version 8.0 will not be required to provide a nasal swab) and urine sample collections for assessments defined in [Appendix 3 : Schedule of Events](#)
- Assessment of AEs
- Diary Review (Dose 1) and Distribution (Dose 2)
- Distribution of epinephrine auto-injectors (2 pack) for participants in the HA/MCD group who did not bring with them or bring expired auto-injectors

Following sample collections, participants will receive their second vaccination. Following vaccination, the study participant will be observed for AEs, including examination of the vaccination site, and have vital sign measurements and additional urine and blood samples collected 1-hour post-vaccination and/or 30-60 minutes after the onset of an allergic reaction. Sample collections post vaccination will be based on participant weight, detailed further in the MOP.

During the 90-minute observation period, all AEs will be recorded, and AEs judged by an investigator to constitute an allergic reaction, even if not severe, will be documented on the appropriate eCRFs. In the event of an allergic reaction, occurring more than 1 hour post vaccination, urine and blood samples will be collected, per [Appendix 3: Schedule of Events](#). Sample collections post vaccination will be based on participant weight, detailed further in the MOP.

In the event of a systemic allergic reaction, participants will be treated with rescue medications ([Section 7.4: Rescue Medications](#)) and observed for a minimum of 2 hours after their symptoms resolve. Vital signs will be monitored during a systemic allergic reaction.

To assist study participants and/or their parents/legal guardians in the identification of and steps to take in the event of an allergic reaction after they leave the study site, each participant will be provided with an Anaphylaxis Emergency Care Plan. The PI or designee shall review the symptoms and steps to take in the event of an allergic reaction, including training on how to use the epinephrine auto-injector, with the participant and/or parents/legal guardians prior to discharge.

#### **9.4.2. Follow-Up Call (Day 25 or 32 ± 1 Day)**

Approximately 3 days following the participant's second vaccination visit, the study team will call the participant to assess for AEs and review the participant diary. Any reported AEs and changes in concomitant medications will be recorded on the appropriate eCRF.

### **9.5. Participants Randomized to Receive Placebo Under Protocol Versions 5.0 – 8.0**

#### **9.5.1. First Vaccination Visit (Day 8; + 14 Days)**

Participants randomized to placebo will be asked to return to clinic to receive their first vaccine injection, approximately 7 days, after they received the placebo. In addition to receiving the Pfizer-BioNTech COVID-19 Vaccine or Moderna COVID-19 Vaccine, the participant will complete the same study procedures as those conducted during the Enrollment Visit, with the exception of growth parameters and pre-vaccination blood sample collections. ([Section 9.2 Enrollment Visit \[Day 1\]](#)). Following vaccination, the study participant will be observed for 90 minutes for AEs, including examination of the injection site, and have vital sign measurements. Participants will have blood collected 30-60 minutes after the onset of an allergic reaction. Sample collections post vaccination will be based on participant weight, detailed further in the MOP.

In addition, the study team will complete a review of the participant's diary and distribute an additional diary, as needed.

#### **9.5.2. Follow-Up Call (Day 11 ± 1 Day)**

Following their First Vaccination Visit, participants randomized to placebo, will have a follow-up call, approximately 3 days later. The study team will call the participant to assess for AEs and review the participant diary. Any reported AEs and changes in concomitant medications will be recorded on the appropriate eCRF.

#### **9.5.3. Second Vaccination Visit (Day 29 or 36; -4 to +14 Days)**

Participants randomized to receive placebo during their Enrollment Visit, will complete a third clinic visit, during which they will receive their second injection of the Pfizer-BioNTech COVID-19 Vaccine or Moderna COVID-19 Vaccine, as assigned.

The following procedures and assessments will be conducted during this visit:

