#### **6.1.1.2. Dosage, Preparation, and Administration**

The Moderna COVID-19 Vaccine multiple-dose vial contains a frozen suspension that does not contain a preservative and must be thawed prior to administration, per the Full FDA EUA Prescribing Information. Additional details are included in the Pharmacy Manual.

For participants 12 years of age or older, the Moderna COVID-19 Vaccine 100 mcg in 0.5 mL will be administered intramuscularly in the deltoid. For participants aged 5 to 11 years, the Moderna COVID-19 vaccine 50 mcg in 0.25 mL will be administered intramuscularly. Vaccine administration details will be recorded on the Vaccine Administration electronic case report form (eCRF).

The Moderna COVID-19 Vaccine is administered as a series of two doses 1 month (28 days) apart.

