#### **6.1.2.2.1. Dosage, Preparation, and Administration**

The Pfizer-BioNTech COVID-19 Vaccine for individuals aged 5 through 11 years multiple-dose vial (up to 10 doses) with orange cap contains a volume of 1.3 mL supplied as a frozen suspension that does not

contain preservative. Each vial must be thawed prior to dilution with 1.3 mL of sterile non-bacteriostatic 0.9% Sodium Chloride Injection, USP and vaccine administration, per the Full FDA EUA Prescribing Information.[13] Additional details are included in the Pharmacy Manual.

The Pfizer-BioNTech COVID-19 Vaccine 10 mcg in 0.2 mL will be administered intramuscularly. Vaccine administration details will be recorded on the Vaccine Administration eCRF.

The Pfizer-BioNTech COVID-19 Vaccine for individuals aged 5 through 11 years is administered intramuscularly as a series of two doses 10 mcg in 0.2 mL each 3 weeks (21 days) apart.

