7.1.2. Assessment Time Windows

Allowable visit windows for all scheduled visits are provided in Appendix 3 of the protocol. In the rare event a vaccination window cannot be met, vaccination may be scheduled beyond the +14-day window. If a participant becomes infected with SARS-CoV-2 or another acute illness following his/her first dose of vaccine, the second vaccination will be delivered, with allowance for a delay up to 90 days following the first dose.

Unscheduled visits may also occur throughout the study.

All data will be included in analyses, regardless of time of assessment. No formal accommodations will be made for out of window visits. Participants who are beyond the 14-day window will be summarized.

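### In the placebo-first arms nothing ties the second-dose window to the actual first-dose date, so the windows read literally admit active doses 3 (Pfizer-BioNTech) or 10 (Moderna) days apart against 21 or 28 stated

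*Protocol*

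**What the plan says.** **Stated interval.** Protocol 6.1.2.2.1 says the Pfizer-BioNTech vaccine for ages 5 to 11 is "administered intramuscularly as a series of two doses 10 mcg in 0.2 mL each 3 weeks (21 days) apart". Section 6.1.2.1.1 gives the same 21 days for ages 12 and over. Section 6.1.1.2 says the Moderna vaccine "is administered as a series of two doses 1 month (28 days) apart". Section 6.1.3.2 carries these schedules over to participants who start with placebo. The note to Figure 2 also counts a Moderna second dose from the first vaccination, but gives no window.

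**No-placebo arms.** Day 1 is the first vaccine dose. Section 9.4.1 places the "second vaccination 21 days (Day 22) or 28 days (Day 29) after their first vaccination", with a window of -4 to +14 days.

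**Placebo-first arms.** Day 1 is the placebo injection, and both vaccine visits are given as study days:

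- Versions 1.0–4.0: "First Vaccination Visit (Day 22 or 29; -4 to + 14 Days" (8.5.1) and "Second Vaccination Visit (Day 43 or 57; -4 to +14 Days" (8.5.3), repeated in Appendix 3, Table B.
- Versions 5.0–8.0: "First Vaccination Visit (Day 8; + 14 Days" (9.5.1) and "Second Vaccination Visit (Day 29 or 36; -4 to +14 Days" (9.5.3). Table D gives the first of these as -4 to +14 instead of +14 only. Section 9.3 puts the first vaccine after placebo within 7 days of Day 1.

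**Checking and reporting.** Sections 8.8 and 9.8 record a deviation when a visit falls outside its window. The only limit they count from the first dose is the 90-day allowance for illness delay. SAP 7.1.2 analyses all data regardless of timing and adds: "Participants who are beyond the 14-day window will be summarized".

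**The concern.** In the no-placebo arms the window protects the stated interval, because the study day and the time since the first vaccine dose run from the same date. In the placebo-first arms they do not. A late first vaccine does not move the second-dose window, so each day of delay can shorten the interval by a day while both visits remain in window. One third of participants are randomised to these arms (2 of 6 under 2:2:1:1; 1 of 3 under 2:1).

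Three things are at stake. The same stated regimen has different permitted intervals by randomised arm. A compressed series would pass the visit-window check and enter the analyses unflagged, since the per-protocol sample has no interval criterion. At the shortest Pfizer-BioNTech intervals, the second dose falls inside the 7-day solicited period of the first. Solicited and later events then become hard to attribute to a dose, and the experience with dose 1 available for review before dose 2 is short.

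**Working it through.** The nominal interval is the target day of dose 2 minus the target day of dose 1. The shortest in-window interval is the earliest day for dose 2 minus the latest day for dose 1; the longest is the latest day for dose 2 minus the earliest day for dose 1.

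**Reproducing the plan's figures.** The nominal days give the stated intervals: 43 - 22 = 21 and 57 - 29 = 28 (versions 1.0–4.0); 29 - 8 = 21 and 36 - 8 = 28 (versions 5.0–8.0). End-of-study days follow as dose 2 plus 7: 50, 64, 36 and 43. The schedule is consistent at its target days; the conflict arises only in the windows.

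**In-window ranges.**

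| Arm and source | Dose 1 days | Dose 2 days | Shortest | Longest |
|---|---|---|---|---|
| No placebo, Pfizer | 1 | 18–36 | 18 - 1 = 17 | 36 - 1 = 35 |
| No placebo, Moderna | 1 | 25–43 | 25 - 1 = 24 | 43 - 1 = 42 |
| Placebo first, v1.0–4.0, Pfizer | 18–36 | 39–57 | 39 - 36 = 3 | 57 - 18 = 39 |
| Placebo first, v1.0–4.0, Moderna | 25–43 | 53–71 | 53 - 43 = 10 | 71 - 25 = 46 |
| Placebo first, v5.0–8.0, Pfizer, 9.5.1 | 8–22 | 25–43 | 25 - 22 = 3 | 43 - 8 = 35 |
| Same, Table D | 4–22 | 25–43 | 25 - 22 = 3 | 43 - 4 = 39 |
| Placebo first, v5.0–8.0, Moderna, 9.5.1 | 8–22 | 32–50 | 32 - 22 = 10 | 50 - 8 = 42 |
| Same, Table D | 4–22 | 32–50 | 32 - 22 = 10 | 50 - 4 = 46 |

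**If Section 9.3 governs versions 5.0–8.0.** The latest day for dose 1 is Day 8, since 8 - 1 = 7. The shortest interval is then 25 - 8 = 17 days (Pfizer-BioNTech) or 32 - 8 = 24 days (Moderna), equal to the no-placebo minima. Section 9.3 does not apply to versions 1.0–4.0.

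**Not only the extreme corner.** With dose 2 on its nominal day, a first vaccine 5 days late leaves 21 - 5 = 16 days (below 17) or 28 - 5 = 23 days (below 24). At the full +14 days late, 21 - 14 = 7 or 28 - 14 = 14 days remain.

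**Overlap.** The solicited period is 7 days including the injection day, so a second dose 3 to 6 days after the first falls within it. That is possible only for Pfizer-BioNTech, since the Moderna minimum is 10 days. The follow-up call is due about 3 days after dose 1, with ±1 day, so at a 3-day interval dose 2 could come before the call.

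**The case against.** The best reply is that the study days are nominal and move with the preceding visit. No sentence says that the windows run from Day 1; that is inferred from the day labels. The literal reading also breaks down elsewhere. Section 9.5.2 sets the call after the first vaccine at Day 11 ± 1, although that dose may fall on Day 22. In the no-placebo arm a second dose on in-window Day 36 would follow its own Day 25 call and Day 29 end-of-study call. Section 6.1.3.2 states the vaccine's own schedule for these participants. This stands as evidence of intent: a reader might infer that the protocol plans doses 3 days apart, and it does not. But the nominal reading is written nowhere, and the window check uses the listed windows.

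A reader might also infer that short intervals are never deviations and never visible. Section 17.1 makes any departure from design or procedures a deviation, which arguably covers a departure from Section 6.1. SAP 6.1 lists deviations, and SAP 6.2 lists administration data by participant. What is missing is a check that would trigger, and a derived interval.

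Nor are the main endpoints blurred. The primary and by-dose endpoints use 90 minutes. The 48-hour endpoint pools both doses and counts events up to 2 days after injection. The priming comparison takes only the first vaccine dose from the placebo arm. The second vaccination visit also includes adverse-event assessment and dose-1 diary review before injection, so dose 1 would still be reviewed, though on a short record.

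**Conclusion.** The contradiction is real and should be resolved. Taken literally, the placebo-first windows permit 3 days (Pfizer-BioNTech) or 10 days (Moderna) between active doses, against 21 or 28 stated and 17 or 24 at minimum in the no-placebo arms. For versions 1.0–4.0, the group used for the SAP's primary analyses, these minima follow from the listed windows. For versions 5.0–8.0 they hold under 9.5.1 or Table D but not under 9.3, and those three passages must themselves be reconciled.

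The result assumes that each window is applied to its listed study day. It describes what the text permits; the documents give no information on intervals in practice. The consequence is limited to attribution of solicited and later events, the length of dose-1 experience available before dose 2, and the absence of any interval summary in the report. It does not undermine the 90-minute endpoints.

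**What to change.** **Protocol.** Reconcile 9.3, 9.5.1, 9.5.3 and Table D with Section 6.1, Section 6.1.3.2 and the Figure 2 note, so that the second-dose window and the stated interval are counted from the same date. Do the same for 8.5.1, 8.5.3 and Table B for the record. This review does not say what the interval or the window should be.

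**SAP 7.1.2.** Derive the actual number of days from active dose 1 to active dose 2 for every participant who received both. Summarise departures on both sides, early and late, by arm, in addition to the planned summary of participants beyond +14 days. For versions 1.0–4.0, where adult enrolment is closed, this is the part that still helps.

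**Cost.** Clarifying wording in the visit sections and schedule tables, one derived variable and one table. Administration data are already listed by participant under SAP 6.2, so no new data collection should be needed.
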